3.2.4. Exploratory Endpoints

3.2.4.1. Blinded Treatment Period

- Proportion of participants able to achieve platelet counts $\geq 50,000/\mu\text{L}$ for 4 out of last 8 weeks of the 24-week treatment period
- Percentage of weeks with platelet count $\geq 50,000/\mu\text{L}$ OR between $\geq 30,000/\mu\text{L}$ and $< 50,000/\mu\text{L}$ and at least doubled from baseline over the 24-week blinded treatment period in the absence of rescue therapy
- Proportion of participants with complete response (defined as platelet count $\geq 100,000/\mu\text{L}$) on 2 consecutive visits at least 5 days apart and no bleeding or rescue ITP therapy use on and through these two visits.
- Proportion of participants with platelet count $\geq 50,000/\mu\text{L}$ on 2 consecutive visits at least 5 days apart and no rescue ITP therapy use on and through these two visits.
- Proportion of participants who have a platelet count that exceeds $250,000/\mu\text{L}$ or $450,000/\mu\text{L}$ (for participants on TPO-RAs)
- Change from baseline in ITP Bleeding Scale (IBLS) assessment at Week 13 and Week 25
- Change from baseline and change from Week 13 on the Fatigue (Item 10 of the ITP-PAQ; physical fatigue), Psychological, Fear, Social Activity, Women's Reproductive Health and Work domains of the ITP-PAQ in adult participants (≥ 18 years) at Week 25
- Change from baseline on the Psychological, Fear, Social Activity, Women's Reproductive Health and Work domains of the ITP-PAQ in adult participants (≥ 18 years) at Week 13
- Change from baseline in QOL as measured by the EuroQOL-5 Dimensions-5 Level (EuroQOL-5D-5L) in adult participants (≥ 18 years)

- Change from baseline in disease-related symptom severity as measured by the Patient Global Impression of Severity (PGIS) scale
- Change from baseline in disease-related fatigue severity as measured by the Patient Global Impression of [Fatigue] Severity (PGIS-Fatigue) scale
- Patient perception of disease-related symptom improvement as measured by the Patient Global Impression of Change (PGIC) scale
- PK parameters as assessed by population pharmacokinetic analysis
- BTK occupancy
- Changes from baseline in TPO levels, T-lymphocytes/ B-lymphocytes/natural killers (T/B/NK) counts, immunoglobulin (IgG, IgG1, IgG4, IgM, IgE) levels
- (Optional) Vaccine-specific IgG response during treatment

See [Appendix 10 \(Appendix 10.5\)](#) for China-specific requirements.

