### **3.2.4 Subgroup analyses**

To assess the homogeneity of the treatment effect across various subgroups, analyses will be performed on the primary endpoint (Definition 1 and Definition 2 respectively) in the adult ITT population across the following subgroups (categories with fewer than 5 participants may be combined with other categories):

- Race (White, Asian, Other)
- Age group (<65 years, ≥65 years)
- Sex (Male, Female)
- Duration of ITP since diagnosis (≤1 year, >1 year to ≤3 years, >3 years)
- Prior splenectomy status (yes, no)
- Baseline platelet counts (<15,000/μL, ≥15,000/μL)
- Prior CS (No prior CS, Prior CS and no concomitant CS, Prior and concomitant CS, Prior CS and concomitant CS and TPO-RA)
- Prior TPO-RA (No prior TPO-RA, Prior TPO-RA and no concomitant TPO-RA, Prior and concomitant TPO-RA, Prior TPO-RA and concomitant TOP-RA and CS)
- Prior intravenous immunoglobulin (IVIg) or anti-D immunoglobulin (Yes, No)
- Prior rituximab (Yes, No)
- Concomitant ITP medications (Yes, No)
- Concomitant ITP medications (CS, TPO-RA, both CS and TPO-RA, neither CS nor TPO-RA)
- US vs. Non-US
- Geographic region:
  - Asia/Pacific (Australia, China, Japan, Singapore, South Korea, Thailand),

- West Europe (Austria, France, Germany, Italy, Norway, Spain, United Kingdom, Netherlands),
- East Europe (Hungary, Israel, Poland, Russia, Turkey, Ukraine),
- North America (Canada, United States),
- South America (Argentina, Brazil, Chile, Mexico).

The observed response rate will be presented along with its associated 95% asymptotic CI in each treatment group and each subgroup. The treatment difference in response rates and its associated 95% CI will be summarized for the subgroups defined above. The treatment difference for each subgroup will likely be estimated via normal approximation without being adjusted by stratification factors due to the expected small cell size. The Mantel-Haenszel estimate of common treatment difference and associated 95% ([Section 3.2.2](#)) adjusted by stratification factors may be considered if appropriate. The analysis method and stratification factors will be specified in the footnote of the corresponding outputs. The consistency of the treatment difference among these sub-populations will be examined by the forest plot.

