## 3.4 TERTIARY/EXPLORATORY ENDPOINT(S) ANALYSIS

### 3.4.1 Definition of endpoint(s)

Please see [Section 1.2.2.4.1](#) and [Section 1.2.2.4.2](#).

Additional details are provided for specific exploratory efficacy endpoints below. Details of COA related endpoints could be found in [Section 3.7.3](#).

*Proportion of participants able to achieve platelet counts  $\geq 50,000/\mu\text{L}$  for 4 out of last 8 weeks of the 24-week treatment period*

Refer to [Section 3.2.1](#).

*Percentage of weeks with platelet count  $\geq 50,000/\mu\text{L}$  OR between  $\geq 30,000/\mu\text{L}$  and  $< 50,000/\mu\text{L}$  and at least doubled from baseline over the 24-week blinded treatment period in the absence of rescue therapy*

Refer to [Section 3.3.1.1](#). For each participant, percentage will be based on the available number of weeks with platelet counts including the weeks censored due to rescue therapy during the double-blind period.

*Proportion of participants with complete response (defined as platelet count  $\geq 100,000/\mu\text{L}$  on 2 consecutive visits at least 5 days apart and no bleeding or rescue ITP therapy use on and through these two visits.*

To qualify for a complete responder, a participant must have met ALL of the following criteria:

- Platelet counts  $\geq 100,000/\mu\text{L}$  on 2 consecutive visits at least 5 days apart, any time from Week 2 to Week 25 and
- No bleeding on and through these two visits (ie, bleeding events identified by SMQ = Haemorrhages via broad and narrow search in eCRF “Adverse Events”);
- Not rescued within the 4 weeks prior to the elevated platelet count and on and through these two visits.

*Proportion of participants with platelet count  $\geq 50,000/\mu\text{L}$  on 2 consecutive visits at least 5 days apart and no rescue ITP therapy use on and through these two visits.*

To qualify for a responder, a participant must have met ALL of the following criteria:

- Platelet counts  $\geq 50,000/\mu\text{L}$  on 2 consecutive visits at least 5 days apart, any time from Week 2 to Week 25 and

- Not rescued within the 4 weeks prior to the elevated platelet count ([Section 3.3.1.1](#)) and on and through these two visits.

*Proportion of participants who have a platelet count that exceeds 250,000/ $\mu$ L or 450,000/ $\mu$ L (for participants on TPO-RA)*

To qualify for a responder, a participant must have met ALL of the following criteria:

- Concomitantly on TPO-RA;

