- Platelet counts  $>250,000/\mu\text{L}$  (or  $>450,000/\mu\text{L}$  respectively) any time from Week 2 to Week 25 and
- Not rescued within the 4 weeks prior to the elevated platelet count ([Section 3.3.1.1](#)).

*Percent change from baseline on CS dose / TPO-RA dose*

Percent of dose change will be calculated at Week 53 (ie, Study day 365  $\pm$  3 days) and after 12 months on the LTE period (ie, Study day 701 ie, Study day 365  $\pm$  14 days).

*Proportion of participants who switch to rilzabrutinib as a monotherapy during the first year of the LTE period*

To qualify for “switching to rilzabrutinib as a monotherapy”, a participant must have stopped the concomitant ITP medication permanently during the first year of the LTE period (ie, from 1st dose during LTE up to Study day 701  $\pm$  7 days).

*Proportion of participants who decrease their CS dose  $>50\%$  relative to baseline values during the first year of the LTE*

Qualified participants are those who have CS dose decrease by  $>50\%$  from baseline during the first year of the LTE period (ie, from 1st dose during LTE up to Study day 701  $\pm$  7 days).

*Proportion of participants who manage to reduce their dose or stop TPO-RA agonists during the first year of the LTE*

Qualified participants are those who have TPO-RA agonist dose decreased or stopped during the first year of the LTE period (ie, from 1st dose during LTE up to Study day 701  $\pm$  7 days).

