### 3.6.3 Additional safety assessments

#### 3.6.3.1 Laboratory variables, vital signs, and electrocardiograms (ECGs)

The following laboratory variables, vital signs, and electrocardiogram (ECG) variables will be analyzed. They will be converted into standard international units and conventional units (as appropriate).

- Hematology
  - Red blood cells (RBC), platelets: red blood cell count, hemoglobin, hematocrit, mean corpuscular volume (MCV), mean corpuscular hemoglobin (MCH), mean corpuscular hemoglobin concentration (MCHC), RBC Morphology, Reticulocyte, Mean platelet volume (MPV), platelet count (efficacy endpoint),
  - Coagulation: prothrombin time, International Normalized Ratio (INR), thrombin time, activated partial thromboplastin time (aPTT), fibrinogen,
  - White blood cells: white blood cell count, neutrophils, lymphocytes, monocytes, basophils, eosinophils
- Clinical chemistry:
  - Metabolism: glucose, total protein, albumin, creatine phosphokinase (screening only),
  - Electrolytes: sodium, potassium, chloride, calcium, phosphorus,
  - Renal function: creatinine, urea (blood urea nitrogen), creatinine clearance (Cockcroft and Gault method) (screening only, for adult participants), estimated glomerular filtration rate (eGFR) (Schwartz method) (screening only, for pediatric participants)
  - Liver function: alanine aminotransferase (ALT), aspartate aminotransferase (AST), alkaline phosphatase, total bilirubin, direct bilirubin and indirect bilirubin
- Urinalysis: pH, specific gravity, protein, glucose, ketones, bilirubin, blood, nitrites, urobilinogen, and leukocytes
- Immunoglobulin Levels: immunoglobulin G (IgG), immunoglobulin G Subclass 1 (IgG1), immunoglobulin G Subclass 4 (IgG4), immunoglobulin M (IgM), immunoglobulin E (IgE)
- Hemolysis panel: direct Coombs (anti-human globulin), haptoglobin

- Thrombopoietin (TPO)
- T-lymphocytes/ B-lymphocytes/natural killers (T/B/NK) counts:
  - CD3+ T Lymphocytes (Absolute), %CD3+ among lymphocytes
  - CD3+CD4+ T Lymphocytes (Absolute), %CD3+CD4+ among lymphocytes
  - CD3+CD8+ T Lymphocytes (Absolute), %CD3+CD8+ among lymphocytes,
  - CD4+/CD8+ T Lymphocyte ratio
  - CD3-CD16/56+ NK Lymphocytes (Absolute), %CD3-CD16/56+ among lymphocytes,
  - CD3-CD19+ B Lymphocytes (Absolute), %CD3-CD19+ among lymphocytes
- Anti-SARS-CoV-2 S protein RBD (Covid-19 vaccine antibody)
- Vital signs: pulse rate, systolic and diastolic blood pressure, respiratory rate, body temperature, weight.

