### **Analyses according to PCSA**

Potentially clinically significant abnormality (PCSA) analyses will be performed based on the PCSA list currently in effect at Sanofi at the time of the database lock ([Section 5.6](#)). For parameters for which no PCSA criteria are defined, similar analyses will be done using the normal range, if applicable. For parameters defined as efficacy endpoints, PCSA summaries will not be provided.

Analyses according to PCSA will be performed based on the worst value during the treatment-emergent period, using all measurements (either local or central, either scheduled, nonscheduled or repeated).

For laboratory variables, vital signs, and ECG variables above, the incidence of participants with at least one PCSA during the treatment-emergent period will be summarized regardless of the baseline level and according to the following baseline status categories:

- Normal/missing
- Abnormal according to PCSA criterion or criteria

For ECG, the incidence of participants with at least one abnormal ECG during the treatment-emergent period will be summarized regardless of the baseline level and according to the following baseline status categories:

- Normal/Not evaluable/Not done
- Abnormal - Not Clinically significant
- Abnormal - Clinically significant

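### SAP 3.4.1 limits both high-platelet proportions (>250,000/µL and >450,000/µL) to TPO-RA users, so no planned table gives these proportions for participants not on a TPO-RA

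*SAP*

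**What the plan says.** The protocol endpoint (synopsis, 3.2.4.1 for the blinded period and 3.2.4.2 for the later periods) is the "Proportion of participants who have a platelet count that exceeds" 250,000/µL or 450,000/µL. A parenthesis referring to participants on TPO-RAs directly follows the second number. SAP 1.2.2.4.1 and 1.2.2.4.2 repeat the endpoint in nearly the same form.

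SAP 3.4.1 turns this into a rule: "To qualify for a responder, a participant must have met ALL of the following criteria". There are three criteria:

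- "Concomitantly on TPO-RA";
- a count above 250,000/µL, or above 450,000/µL for the second proportion, at any time from Week 2 to Week 25;
- "Not rescued within the 4 weeks prior to the elevated platelet count".

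On abnormal laboratory values, SAP 3.6.3.1 states: "For parameters defined as efficacy endpoints, PCSA summaries will not be provided". The laboratory list in the same section carries the entry "platelet count (efficacy endpoint".

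**The concern.** The operational definition is narrower than at least one natural reading of the protocol. Where the parenthesis sits, it suggests a separate, higher threshold for TPO-RA users, with 250,000/µL applying to the others or to everyone. The SAP instead makes TPO-RA use a condition for both thresholds and gives no reason. Neither its version history (Table 1) nor its list of protocol changes (Table 11) mentions a restriction.

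The participants left out are a planned part of the trial. The subgroup list in SAP 3.2.4 includes "Concomitant ITP medications (CS, TPO-RA, both CS and TPO-RA, neither CS nor TPO-RA", so two of its four categories contain no TPO-RA. In those participants a very high count is not confounded by a second platelet-raising drug, so they are a group in which a reader would want to see the proportion. As the SAP stands, the report would not contain it.

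**Working it through.** No arithmetic in the plan bears on this point. The check is to apply the SAP rule to example participants and then look for any other output that would give the same information. The counts are illustrative, and no participant is rescued in the preceding 4 weeks.

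**Step 1. The rule as a logical AND.** A participant is counted only if on a TPO-RA AND above the threshold AND not recently rescued.

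| Participant | Count | >250,000/µL | >450,000/µL |
|---|---|---|---|
| On TPO-RA | 500,000/µL | counted | counted |
| Corticosteroid only | 500,000/µL | not counted | not counted |
| Neither drug | 700,000/µL | not counted | not counted |

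**Step 2. The protocol wording.** Three readings are possible:

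- (a) 250,000 for everyone and 450,000 for TPO-RA users;
- (b) 250,000 for non-users and 450,000 for users;
- (c) both thresholds for users only.

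Under (a) and (b) the second and third participants are counted at 250,000. Only (c) gives the SAP result.

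**Step 3. Other outputs that could show a high count off a TPO-RA.**

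- *Laboratory abnormality (PCSA) tables.* SAP 5.6.1 has a platelet criterion of at least 700 Giga/L. Since 1 Giga/L = 1,000/µL, this is 700,000/µL. The efficacy-parameter exclusion removes it. Even if kept, it lies above both thresholds, because 700,000 > 450,000 > 250,000.
- *By-visit laboratory statistics.* SAP 3.1 includes the maximum, with no TPO-RA condition. A group maximum does not say how many participants exceeded a value. SAP 3.6.3.1 uses central measurements only. Weeks 2 to 25 contain 24 weekly visits, and the clinic visits with central samples are Weeks 5, 9, 13, 17, 21 and 25. The summary therefore draws on at most 6 of 24 scheduled counts (6/24 = one quarter). SAP Table 11 says platelet testing moved to local laboratories because central hematology samples were prone to clotting. Footnote d of Table 9 limits the descriptive summary to selected tests, whereas the section text promises all laboratory variables.
- *Adverse events.* Protocol 9.3.8 requires symptoms, a change in study drug or a change in concomitant therapy. Protocol 9.3.2 allows an isolated out-of-range value not to be an adverse event. A high count without symptoms can go unrecorded.
- *Complete response.* The threshold of 100,000/µL covers everyone but does not separate intended from very high counts.

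**Step 4. Later periods.** The endpoint is also listed for the open-label and long-term extension periods, but the SAP 3.4.1 definition ends at Week 25. Protocol Section 4 allows TPO-RA withdrawal in the extension under stated conditions. If the same criterion were carried forward, participants who stop the TPO-RA would drop out of the count.

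**The case against.** The strongest reply is that the protocol parenthesis is ambiguous and the SAP is entitled to settle it. Grammatically it can cover both numbers. Two nested thresholds in one population are not a sign of error either: the ALT categories in SAP 5.6.1 are nested and described as cumulative. A reader might infer that the protocol plainly assigns 250,000 to non-users and 450,000 to users. The documents do not say so, and the point should not rest on it. What survives is that the SAP chose the narrowest reading without stating that it had made a choice.

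A reader might also infer that a high count off a TPO-RA is never reported at all. That goes too far. It could appear as a group maximum in the by-visit statistics or as an adverse event if clinically significant, and thromboembolic events are tabulated regardless of background drug. The gap is the missing number or proportion above a threshold.

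Finally, the endpoint is exploratory, and neither document states that its purpose is to detect overshoot. Entry requires average counts below 30,000/µL, and Protocol 2.6 reports a mean rise of 22.5 × 10⁹/L after 28 days at the trial regimen. Counts above 250,000/µL may therefore be uncommon. A mean does not exclude outliers, but this argues against attaching any figure to the loss.

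**Conclusion.** The point holds as a mismatch between an operational definition and its protocol endpoint. Under SAP 3.4.1 the numerator off a TPO-RA is zero by construction at both thresholds, and no other planned table supplies the number or proportion. This follows from the text and needs no numerical assumption.

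The size in participants is unknown. The documents give neither the share without a TPO-RA nor the rate of counts above 250,000/µL, and SAP 3.4.1 states no denominator, so an estimate of missed cases would be invented. The endpoint is exploratory and SAP 3.4.2 plans no tests on it; the primary and key secondary results, alpha and power are not affected. It is worth correcting because a reported result changes and the correction is cheap.

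**What to change.** In SAP 3.4.1, delete concomitant TPO-RA use as a qualifying criterion and use it as a reporting category. Give the proportions above 250,000/µL and above 450,000/µL separately for participants on and not on a concomitant TPO-RA, each over its own stated denominator, and overall. This layout serves every reading of the protocol parenthesis. The categories already defined in SAP 3.2.4 can be collapsed to on/off. Align the endpoint wording in the protocol and SAP 1.2.2.4, and state how the definition applies after Week 25.

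The cost is a short wording change and a few extra descriptive rows. Platelet counts and concomitant medication are already collected.

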- b At the Week 13 visit review previous platelet counts for response during the first 12 weeks. If the participant met the criteria for response continue with the Week 13 visit assessments, the participant should continue in the blinded part. If the participant did not meet the criteria for response, complete the Week 25 visit assessments and the participant may start the open label period or discontinue from the study. Platelet response is defined as a) a platelet count of $\geq 50,000/\mu\text{L}$ OR a platelet count of between $\geq 30,000/\mu\text{L}$ and $< 50,000/\mu\text{L}$ and at least doubled from baseline at any time during the first 12 weeks and b) absence of rescue medication in the 4 weeks prior to the latest elevated platelet count that meets platelet response criteria.) Participants who receive rescue medication during the last 12 weeks also may join the open-label part or discontinue from the study. See [Figure 1](#) for decision tree for assessing response at Week 13 and for calculation of baseline platelet count.
- c For pediatric participants (see [Appendix 10.7](#) for EU [EEA countries] age ranges) height is recorded at Screening, Week 13, Week 25, Week 37, and Week 53. For participants aged 18 years and older height is recorded at Screening only.
- d Full physical examination at Screening, 4-week follow-up and early termination; abbreviated physical examination at all other visits. Medical history should include vaccine history. See [Appendix 10.6](#) for Italy-specific requirements.
- e ECG for pediatric participants (see [Appendix 10.7](#) for EU [EEA countries] age ranges) will be performed predose and 2 hours postdose (± 15 mins) at the Week 1 and Week 25 visits.
- f Urinalysis: pH, specific gravity, protein, glucose, ketones, bilirubin, blood, nitrites, urobilinogen, and leukocytes.
- g Participants enrolled with positive HBV core antibody test result and HBsAb titer ≥ 100 IU/L will have HBV DNA monitored monthly while on treatment and for 6 months after treatment has ended.
- h For women of childbearing potential only. Serum pregnancy test must be performed at Screening; a urine pregnancy test must be performed at all other study timepoints.
- i To confirm postmenopausal status for women who are not surgically sterile and of reproductive potential.
- j Historical lab results may be used for ABO and Rh Blood Type.

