- l QOL Questionnaires include EQ-5D-5L, ITP-PAQ or ITP-KIT, and PGIS-Fatigue/PGIS/PGIC. ITP-PAQ, EQ-5D-5L and PGIS-Fatigue/PGIS/PGIC (in that order) will be administered for adults 18 years or older. ITP-KIT and EQ-5D-5L (in that order) will be administered for pediatric participants (see [Appendix 10.7](#) for EU [EEA countries] age ranges). **Questionnaires should be completed prior to all other study procedures and interactions with site staff.**
- m See [Appendix 10](#) for country-specific requirements.
- n Optional collection of 2 blood samples for vaccine-specific IgG in serum (see [Section 7.9.9](#) for a list of routine vaccines). The first blood sample should be collected within 6 weeks prior to each vaccine dose regimen and the second blood sample should be collected within approximately 3 to 6 weeks after the vaccine dose regimen is complete. Whenever possible, blood for vaccine-specific IgG should be collected at a scheduled visit; but may also be collected during an Unscheduled Visit. Dates of vaccination, disease, brand name of vaccine product and antigenic strain should be recorded.
- o Week 25/SD169 visit is the last visit of the blinded treatment period and may also serve as the start of the open label period.
- p For participants who will enter the open label period directly after 12 weeks of blinded treatment, they will attend the Week 13/SD85 visit which corresponds to the Week 25/SD169 visit (Table 2), this would be their last visit of the blinded treatment period and also the start of the open label period. They will follow the open label period schedule of assessments from Week 29 (Table 2) starting at their next scheduled visit for a total of 28 weeks.
- q For participants who will enter the open label period directly after 12 weeks of blinded treatment, they will follow the open label period schedule of assessments (**Week 25 to Week 53**) which means that they will be treated on the open-label part for a total of 28 weeks. After Week 53, the participants will follow the schedule of assessments according to their eligibility for the LTE period.

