4. STUDY DESIGN

This is a global, randomized, parallel-group, double-blind, multicenter clinical study in patients with primary ITP who had a response to either IVIg or CS that was not sustained.

After providing informed consent, participants will enter a 28-day screening period. Upon completion of the screening period, participants who satisfy all the inclusion criteria and none of the exclusion criteria of this protocol will be randomized in a 2:1 allocation ratio to one of two study arms: rilzabrutinib or placebo. Randomization will be carried out separately for the two age groups. For the adult group, stratified permuted block randomization will be implemented; for the pediatric group, dynamic randomization algorithm (minimization) will be implemented. The factors used for stratification (for adult participants), or balance (for pediatric participants) are splenectomy status (yes/no), and by severity of thrombocytopenia (Inclusion Criteria #3 platelet counts $<15,000/\mu\text{L}$ or $\geq 15,000/\mu\text{L}$).

[figure not shown]
After randomization, participants will start a blinded treatment period of up to 24 weeks followed by an open label period of 28 weeks during which all participants will receive rilzabrutinib, and then a 4-week safety follow-up period or LTE.

At the end of 12 weeks of treatment, participants will be assessed for achieving a platelet response defined as a) platelet count of $\geq 50,000/\mu\text{L}$ OR a platelet count of between $\geq 30,000/\mu\text{L}$ and $<50,000/\mu\text{L}$ and at least doubled from baseline at any time during the first 12 weeks and b) absence of rescue medication in the 4 weeks prior to the elevated platelet count that meets platelet response criteria.

Figure 1 depicts the decision process for assessing response. The baseline value of platelet count is defined as the average of all the participant's Predose platelet counts (Screening and Study Day 1).

- Participants who respond will continue the blinded treatment period for a total of 24 weeks before entering the open label period.
- Participants who do not respond (including participants who receive rescue medication after 8 weeks of treatment) may discontinue from the study or enter the 28-week open label period at the end of Week 12, receiving treatment with 400 mg BID of rilzabrutinib. The Initial study medication assignment will remain blinded.

Figure 1 - Decision tree for assessing response at Week 13

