6.6.2. Particular Permissible Medications

The following medications are permitted for use during the study:

- ITP medications, an oral CS and/or a TPO-RA (authorized for the treatment of ITP)

Note:

- These medications must be maintained at stable doses from 14 days before Study Day 1 and until the last dose of study medication. Adjustments in the doses of concomitant ITP medications will be permitted for associated safety concerns only.
- Administration of corticosteroids and TPO-RAs should follow corresponding updated package inserts/SmPCs of the marketing authorization.
- Tapering is allowed during LTE period only due to achieving durable platelet response, and would follow the following guidelines with 2 weekly platelet counts between tapers:
 - 10 mg/day every one to two weeks from an initial dose >40 mg of prednisone or equivalent per day
 - 5 mg/day every one to two weeks at prednisone doses ≤ 40 to >20 mg or equivalent per day
 - 2.5 mg/day every one to two weeks at prednisone doses ≤ 20 to >10 mg or equivalent per day
 - 1 mg/day every one to two weeks at prednisone doses ≤ 10 to >5 mg or equivalent per day
 - 0.5 mg/day every one to two weeks at prednisone doses ≤ 5 mg or equivalent per day down to zero. This can be achieved by alternating daily doses (eg, 5 mg on day one and 4 mg on day two)
 - Dose of corticosteroid can be up titrated if platelet counts fall below $50,000/\mu L$ on two consecutive measurements
- IVIg or high- dose CS, platelet infusion, or anti-D immunoglobulin infusion as rescue medications

- Clinically relevant drugs that are substrates of CYP3A, including those considered to be sensitive CYP3A substrates. Appropriate caution should be used when co-administering sensitive CYP3A substrates with rilzabrutinib, including an assessment of medical risk-benefit for each medication. Consideration should also be given to avoidance of high doses, dose reduction, or replacement of sensitive CYP3A substrate drugs
- H₂ receptor blocking drugs (ranitidine or famotidine) and antacids are permitted provided they can be given 2 hours or more after administration of rilzabrutinib or placebo

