**Table 12 - Analysis window definition for unscheduled measurements**

Scheduled Visit	Targeted study day (Analysis window) for Platelet Count a	Targeted study day (Analysis window) for Others b
Week n c	1+7*(n-1) (+/-3)	-
Week 5	29 (+/-3)	29 (-13, +14)
Week 9	57 (+/-3)	57 (-13, +14)
Week 13	85 (+/-3)	85 (-13, +14)
Week 17	113 (+/-3)	113 (-13, +14)
Week 21	141 (+/-3)	141 (-13, +14)
Week 25	169 (+/-3)	169 (-13, +14)
Week 29	197 (+/-3)	197 (-13, +14)
Week 33	225 (+/-3)	225 (-13, +14)
Week 37	253 (+/-3)	253 (-13, +14)
Week 41	281 (+/-3)	281 (-13, +14)
Week 45	309 (+/-3)	309 (-13, +14)
Week 49	337 (+/-3)	337 (-13, +14)
Week 53	365 (-3, +14)	365 (-13, +14)
Month 1 LTE	393 (-13, +14)	393 (-13, +14)
Month 2 LTE	421 (-13, +14)	421 (-13, +14)
Month 3 LTE	449 (-13, +14)	449 (-13, +14)

Scheduled Visit	Targeted study day (Analysis window) for Platelet Count a	Targeted study day (Analysis window) for Others b
Month 4 LTE	477 (-13, +14)	477 (-13, +14)
Month 5 LTE	505 (-13, +14)	505 (-13, +14)
Month 6 LTE	533 (-13, +14)	533 (-13, +14)
Month 7 LTE	561 (-13, +14)	561 (-13, +14)
Month 8 LTE	589 (-13, +14)	589 (-13, +14)
Month 9 LTE	617 (-13, +14)	617 (-13, +14)
Month 10 LTE	645 (-13, +14)	645 (-13, +14)
Month 11 LTE	673 (-13, +14)	673 (-13, +14)
Month 12 LTE	701 (-13, +42)	701 (-13, +42)
QX_LTE where X=1,2,3,....	701+28*3*X for X=1,2,3,.... (-41, +42)	

Study days are calculated considering Day 1 as the day of first administration of intervention (or the day of randomization for participant not exposed).

a Applicable to hematology, differential, reticulocytes. Hematology are measured weekly up to protocol Week 53, then every 4 weeks for 1 year, then quarterly afterwards.

b Applicable to parameters other than hematology, differential, reticulocytes.

c n = 2-4, 6-8, 10-12, 14-16, 18-20, 22-24, 26-28, 30-32, 34-36, 38-40, 42-44, 46-48, 50-52.

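### SAP 3.4.1 fixes Week 53 at Study day 365 and LTE month 12 at Study day 701 for everyone, about 84 days late for participants who enter open label at Week 13

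*SAP*

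**What the plan says.** SAP 3.4.1 ties the exploratory medication endpoints to study days. For percent change in CS or TPO-RA dose it states: "Percent of dose change will be calculated at Week 53 (ie, Study day 365", with a window of ±3 days. The later reading is Study day 701, which the same sentence then equates with Study day 365 ± 14 days. Three LTE proportions (switch to monotherapy, CS dose cut by more than half, TPO-RA reduced or stopped) are counted from the first "dose during LTE up to Study day 701", ±7 days.

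The footnote to SAP Table 12 sets the origin: "Study days are calculated considering Day 1 as the day of first administration of intervention". Nothing resets the count at open-label or LTE entry.

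The protocol does not put everyone on that calendar. Under Section 4, participants without a platelet response "may discontinue from the study or enter the 28-week open label period at the end of Week 12". Table 2 footnote p (Synopsis) says "they will attend the Week 13/SD85 visit which corresponds to the Week 25/SD169 visit", and that they then follow the open-label schedule "starting at their next scheduled visit for a total of 28 weeks". Section 4 also lets participants who stop blinded treatment between Weeks 13 and 24 join open label at their next scheduled visit.

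On dose changes, protocol 6.6.2 states: "Tapering is allowed during LTE period only due to achieving durable platelet response".

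**The concern.** SAP 1.2.2.4.2 describes these endpoints by period: the end of open label (Week 53) and 12 months into the LTE. SAP 3.4.1 turns those periods into fixed days that suit only a participant who completes 24 weeks of blinded treatment. For anyone who switches early, the named day and the named period come apart.

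Two things are at stake. The Week 53 dose-change summary would pool values read at the end of open label with values read well after it. The first-year LTE proportions would pool participants observed for different lengths of time, and a longer window gives more chance to qualify. Early switching is driven by non-response in the blinded period, so the discrepancy is unlikely to fall evenly across the randomized groups.

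**Working it through.** **Inputs.** Target day for Week n is 1 + 7(n − 1) (SAP Table 12). Open label lasts 28 weeks = 196 days (protocol Section 4; Table 2 footnotes p and q). LTE months are 28 days apart in Table 12, so 12 months = 336 days. The Week 13 visit window is ±3 days (protocol Table 1). The End of Study visit is 4 weeks after the last dose.

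**The SAP's own figures.** Week 25 = 1 + 7×24 = Day 169. Week 53 = 1 + 7×52 = Day 365. LTE month 12 = 365 + 336 = Day 701. Both stated days reproduce for a 24-week completer.

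**Early switchers.** Week 53 = switch day + 196; month 12 = that day + 336; window length = 701 − Week 53 day. The Week 17 and Week 21 rows assume that the 28-week open-label period also applies to them.

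| Open-label start | Week 53 | Offset from Day 365 | LTE month 12 | Days from LTE entry to Day 701 |
|---|---|---|---|---|
| Week 25, Day 169 | 365 | 0 | 701 | 336 |
| Week 21, Day 141 | 337 | 28 | 673 | 364 |
| Week 17, Day 113 | 309 | 56 | 645 | 392 |
| Week 13, Day 85 | 281 | 84 | 617 | 420 |

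With the Week 13 visit between Days 82 and 88, the offset runs from 169 − 88 = 81 to 169 − 82 = 87 days.

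**Dose change at Week 53.** Day 365 ± 3 spans Days 362 to 368, which excludes Day 281. For a Week-13 switcher, Day 365 is 84 days (12 weeks) after open label ends. If the participant entered the LTE, the reading is an LTE value. If not, End of Study was near Day 281 + 28 = 309, so Day 365 lies 56 days after the last study visit and there is no on-study dose to read.

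**First-year LTE proportions.** 420 days (60 weeks) against 336 days (48 weeks), a ratio of 420/336 = 1.25.

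**Table 12.** For a Week-13 switcher, Day 281 (true Week 53) is the Table 12 target day for Week 41, and Day 617 (true LTE month 12) is the target for Month 9. An unscheduled count on Day 225 is 225 − 85 = 140 days, or 20 weeks, into open label. That is nominal Week 45, but Table 12 assigns Day 225 to Week 33.

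**The case against.** The strongest reply is that most of the SAP does not run on study days. The open-label and LTE populations (Section 2), the period boundaries (3.1) and the stability endpoint (3.3.2.1) use nominal visits or actual first doses. Section 5.4 says a scheduled measurement is used whenever there is one, and Table 12 is titled for unscheduled measurements. This stands. It confines the Table 12 problem to fallback values, although the lead-in to the table speaks of scheduled as well as unscheduled visits and leaves its scope unclear. It does not rescue 3.4.1, where the endpoint is a medication dose and the study day itself locates the reading.

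A second reply concerns tapering. A reader might infer that the Day 365 reading is heavily contaminated by LTE tapering. Protocol Section 4 and Table 3 footnote a require qualifying counts at three scheduled visits over 12 weeks before a response-driven reduction. If those visits are counted from LTE entry on Day 281, that point is reached at about Day 365. Other LTE dose changes are permitted with no clear waiting time, so some contamination is possible, but the documents do not support calling it large.

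Two further inferences go too far:

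- **Open-label durable response in former placebo participants.** SAP 1.2.2.4.2 defines it on weekly scheduled counts in the last 16 weeks of the open-label period. It is not shown to use misplaced counts, apart from any unscheduled substitutes.
- **Item 10 fatigue at Week 13.** Table 1 footnote b tells non-responders to "complete the Week 25 visit assessments and the participant may start the open label period or discontinue from the study", so one might fear that the Day 85 score is filed as Week 25 and imputed at Week 13. But Table 2 footnote p calls this the Week 13 visit and the last blinded one, and Day 85 is the centre of the Week 13 window (Days 72 to 99). An explicit mapping sentence would help; an error is not shown.

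**Conclusion.** The point holds for four exploratory endpoint definitions in SAP 3.4.1 (percent change in CS or TPO-RA dose, and the three first-year LTE proportions) and for fallback allocation under Table 12 in open label and LTE. The size is 84 days for a Week-13 switcher (81 to 87 with the visit window), 56 or 28 days for a switch at Week 17 or 21, and an LTE window 25% longer at most on target days. This rests on reading 3.4.1 literally and on a full 28-week open-label period.

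The number affected cannot be given. The documents do not state how many will switch at Week 13. The LTE proportions concern only those who complete open label with the required platelet response, and the dose endpoints need concomitant CS or TPO-RA at baseline.

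SAP 3.4.2 makes the exploratory analyses mainly descriptive, with no testing. No effect on the primary or key secondary tests is shown. The text should be corrected before the open-label and LTE analyses, but it does not bear on the confirmatory result.

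**What to change.** In SAP 3.4.1 and Table 12:

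- Define open-label time points by nominal visit, or by days from first open-label dose (OL Day 1 = nominal Week 25; Week 53 = OL Day 197, since 365 − 169 + 1 = 281 − 85 + 1 = 197).
- Define LTE time points from the first LTE dose or the LTE entry visit (month 12 = LTE Day 337, since 336 + 1 = 337), and end the first-year window there for everyone.
- Limit the grid counted from first dose to double-blind data, and state whether Table 12 governs scheduled visits or only unscheduled ones.
- Correct the sentence that equates Study day 701 with Study day 365, and reconcile the windows in 3.4.1 (±3, ±14 and ±7 days) with Table 12 (−3/+14 for platelets and −13/+14 for other parameters at Week 53; −13/+42 at LTE month 12).
- As a clarification, add one sentence assigning the Day 85 switch visit to Week 13 in double-blind by-visit analyses.

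The cost is SAP wording and re-derivation of analysis days. No new data are needed.
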